4.2.2. Other Secondary Efficacy Endpoints

4.2.2.1. Time to Progression (TTP)

Time to progression (TTP) is defined as the time from date of randomization until ICR-determined PD per RECIST v.1.1, or death due to disease progression, whichever occurs first. TTP outcome and censoring definitions are similar to the outcome and censoring definitions for PFS in Table 4-1, with the only exception that only death due to disease progression will be considered a TTP event. Death due to reasons other than disease progression will be a new censoring event under situation #5.

TTP on patient's last prior systemic therapy is defined as time since start of last prior systemic therapy to date of disease progression. For patients without a disease progression date, their TTP will be censored on the discontinuation date of last prior systemic therapy.

The comparison of TTP on study treatment to TTP on last prior therapy will be performed using a stratified Cox proportional hazards regression model stratifying on patient IDs to account for correlation within patient. This analysis will be conducted respectively among Ph3-ITT and Ph2-ITT patients randomized to selinexor.

For exploratory purpose, TTP will be summarized among Ph3-ITT patients randomized to placebo arm, Ph3-OL population, Ph2-ITT patients randomized to placebo arm, and Ph2-OL population respectively. For open-label selinexor, TTP is measured as time since the start of open-label treatment until ICR-determined PD per RECIST v.1.1, or death due to disease progression, whichever occurs first. Median TTP time with 95% CIs will be presented using the KM method.

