|---|--------------------------|----------------------|
| Karyopharm Therapeutics Inc. | Selinexor (KPT-330) | Phase 2-3 |
| 
analysis was conducted by both WHO and RECIST v. 1.1 Criteria and served as a guideline to inform the final design of the Phase 3 portion of the study.
 
At the time of the preliminary PFS analysis, there were 48 events by WHO (22 selinexor, 26 placebo) and 28 events by RECIST v.1.1. (10 selinexor, 18 placebo). Both analyses showed trends favoring selinexor over placebo, while RECIST v. 1.1 results show a more significant effect size (hazard ratio [HR] of 0.84, 95% CI [0.47, 1.49] by WHO as compared with HR of 0.60, 95% CI [0.28, 1.31] by RECIST v. 1.1). A Landmark analysis based on RECIST v. 1.1 for patients continuing on study after 45 days showed a more significant HR of 0.24 (95% CI [0.05, 1.15]) in favor of selinexor.
 
Of the 57 patients in Phase 2, 56 met the eligibility criteria for the study. The formal primary Phase 2 PFS analysis will be performed on all 56 eligible patients randomized to study treatment in Phase 2 when their treatment assignments are unblinded. Phase 2 patients will be analyzed in the treatment arm to which they are randomized.
 
Phase 3:
 
The final efficacy analysis will be conducted among Phase 3 patients only.
 
Phase 3 Primary Endpoint Analysis
 
The primary PFS analysis will be performed on the intent-to-treat (ITT) population for Phase 3 patients and on the per-protocol (PP) population as a supportive analysis. The stratified log-rank test will be used to test the null hypothesis that the PFS distributions are the same for both treatment groups versus the alternative hypothesis that the duration of PFS for the selinexor arm is longer than the placebo arm using a 1-sided test and alpha=0.025 level of significance, adjusted using the Cui, Hung, and Wang (CHW) method (Cui 1999).
 
Phase 3 Sample Size and Statistical Power
 
Per protocol, the Phase 3 sample size was re-evaluated based on the Phase 2 results. Sample size calculations were conducted under the following assumptions:
 
CCI
 
Based on these assumptions, approximately 277 eligible patients will be randomized to receive either selinexor (60 mg twice weekly) or placebo in a blinded manner to observe 209 PFS events.
 
CCI
 | | |
| [REDACTED] | | |

Table 1: Schedule of Assessments and Study Activities: Blinded Phase 2 and Phase 3

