8.3. Inclusion Criteria

Patients eligible for inclusion in this study must meet all of the following criteria:

1. Written informed consent in accordance with national, local, and institutional guidelines obtained prior to any screening procedures
2. Must be willing and able to comply with the protocol
3. Patients ≥ 12 years of age (patients <18 years of age are permitted only in countries in which adolescents have been approved by the national/local regulatory/ethical authority).
4. Patients with a body surface area (BSA) $\geq 1.2 \text{ m}^2$ as calculated per [Dubois 1916](#) or [Mosteller 1987](#).
5. Documented histologic evidence of DDLS at any time from initial diagnosis to randomization AND current evidence of DDLS requiring treatment (documented evidence of disease progression from the most recent treatment):
 - Documentation of histologic evidence of DDLS requires the following:
 - This information will be provided based on prior diagnostic testing and is required for randomization.
 - Tissue (fresh or archival) will be provided for confirmatory histology at a central laboratory but confirmatory results are not required prior to randomization.
 - If archival tissue > 12 months old, the quality of the sample for confirmatory histology must be confirmed by the site histopathologist prior to randomization.
6. Must have measurable disease according to:
 - The bidimensional WHO Response Criteria ([Miller 1981](#)) (Phase 2 patients only)
 - RECIST v. 1.1 ([Eisenhauer 2009](#)) ([Phase 3 patients only](#))
7. Radiologic evidence of progressive disease (PD) within 6 months prior to randomization. If the patient received other intervening therapy after PD is documented, further PD must

be documented after the completion of the intervening therapy, with the exception of patients who discontinued most recent treatment after no more than 1 dose.

8. Must have received at least 2 but no more than 5 prior systemic therapies for the treatment of liposarcoma.
9. Patients should have recovered from all major surgery, radiation or other interventions ≥ 21 days prior to randomization. Patients must have recovered from any clinically significant therapy-related toxicity to \leq Grade 1 per CTCAE v. 4.03. Minor procedures, such as biopsies, dental work, or placement of a port or intravenous line for infusion, are permitted.

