14.3.4.2.2. Phase 3 Secondary Key and Efficacy Endpoint Analysis

Secondary Key Endpoint Analysis

Key secondary variables will include the following, assessed in hierarchical fashion in the order presented (to preserve the overall Type I error for the study), according to the definitions described in the objectives and study endpoints:

- OS for non-inferiority
- OS for superiority

OS endpoints will be analyzed using the stratified log-rank test as described above. In sensitivity analysis for OS, the 2-stage estimation method will be implemented to assess the impact of cross-over on the effect of selinexor on OS ([Latimer 2017](#), [Latimer 2018](#)).

Secondary Efficacy Endpoint Analysis

The comparison of TTP in the current study to TTP on the most recent prior therapy will be performed as time-to-event using a stratified log-rank test stratified by patient IDs to account for correlation within patient and adjusted for treatment arm. Note that TTP for the current study may represent censored results, therefore, to minimize the impact of censoring, this analysis may require maturation of the TTP data beyond the required time at which the number of events for the primary PFS analysis at the end of Phase 3 have occurred.

Comparison of ORR between the two treatment arms will be performed using the Cochran-Mantel-Haenszel (CMH) χ^2 or exact test as appropriate, stratified by the randomization stratification factors. For OS, an additional descriptive comparison of the median OS from the randomized selinexor arm will be made to historical OS to the extent feasible, to assist in providing the proper context for the ITT analysis of selinexor versus placebo.

[figure not shown]
DOT and PFS according to the Investigator will be analyzed using the stratified log rank test as described above.

QoL Analysis

[figure not shown]
The QoL endpoint as assessed by the EORTC QLQ-C30 and EuroQoL EQ-5D-5L questionnaires will be analyzed as a total score, using a linear mixed effects model with fixed effect of treatment arm, randomization stratification factors, and the baseline value for the parameter in the model as a covariate, as well as random effect of subjects and repeated measures over time points. For EORTC QLQ-C30 the transformed score will be used, calculated according to the *EORTC QLQ-C30 Scoring Manual*. For the EuroQoL EQ-5D-5L questionnaire, the overall health score will be used.

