4.2.2.5. Time to Next Treatment (TTNT)

[figure not shown]
TTNT is defined as time since randomization until the first new antineoplastic therapy or death due to any cause, whichever occurs first. For patients without an event, their follow-up time will be censored at the date of discontinuation from the study, or date of last participating visit (e.g., a telephone contact with patient status being alive) on or before database cut-off date, whichever occurs first.

TTNT on patient's last prior systemic therapy is defined as time since start of last prior systemic therapy to start of blinded study treatment or death due to any cause, whichever occurs first. For patients who were randomized but never received study treatment, and did not die before discontinuation from study, their follow-up time will be censored at the date of discontinuation from the study, or date of last participating visit (e.g., a telephone contact with patient status being alive) on or before database cut-off date, whichever occurs first.

[figure not shown]
The analysis comparing TTNT on study treatment vs. on last prior systemic therapy will be conducted among patients in the Ph3-ITT population randomized to selinexor and placebo arms separately. To account for within-person correlation, a stratified Cox proportional hazards model analysis will be conducted stratifying on patient IDs. KM median TTNT times with 95% CIs, and KM curves will be provided.

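### SAP 4.2.2.1 compares TTP on study with TTP on the last prior therapy in the selinexor arm only, so that hazard ratio cannot be read as a drug effect

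*SAP*

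**What the plan says.** Comparing TTP on study treatment with TTP on the last prior systemic therapy is a secondary objective in both phases (protocol 6.1.2 and 6.2.2; SAP 1.2.1.2 and 1.2.2.2).

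- **SAP 4.2.2.1, the two records.** On-study TTP is the "time from date of randomization until ICR-determined PD per RECIST v.1.1, or death due to disease progression, whichever occurs first". Prior TTP is the "time since start of last prior systemic therapy to date of disease progression", with no reader, criteria or scan interval given.
- **SAP 4.2.2.1, the model.** A Cox model stratified by patient ID compares the two records. Its scope is: "This analysis will be conducted respectively among Ph3-ITT and Ph2-ITT patients randomized to selinexor". For placebo the section says only: "For exploratory purpose, TTP will be summarized among Ph3-ITT patients randomized to placebo arm". That is a Kaplan-Meier summary with no prior-therapy comparison.
- **Protocol 14.3.4.2.2.** The same comparison is a "stratified log-rank test stratified by patient IDs to account for correlation within patient and adjusted for treatment arm", which implies that both arms are in the analysis.
- **SAP 4.2.2.5.** The parallel comparison for time to next treatment (TTNT), also stratified by patient ID, is run "among patients in the Ph3-ITT population randomized to selinexor and placebo arms separately".
- **SAP 1.7 and 1.8.** Neither lists the restriction to selinexor as a change. The blacked-out bullets in 1.7 are introduced as endpoints dropped for lack of data, so they are not a likely place for it.
- **Protocol 14.3.4.2 and SAP 4.2.** The protocol names TTP among the endpoints compared between arms by stratified log-rank test. The SAP's general rule for secondary time-to-event endpoints says the same without naming TTP.

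**The concern.** A before-and-after comparison within patients isolates a drug effect only if the drug is all that differs between the two records. Here three other things differ.

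- **Line of therapy.** The study record always comes later in the disease course.
- **Selection.** Inclusion criterion 5 in protocol 8.3 requires "documented evidence of disease progression from the most recent treatment", and criterion 7 requires radiologic progression within 6 months of randomization. The prior record is therefore selected on having failed; the study record is not.
- **Assessment.** On-study progression is read centrally by RECIST 1.1 at weeks 6, 12, 18 and 24 and then every 12 weeks. Prior progression comes from the medical history (protocol 10.3).

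In selinexor patients alone, all of this is folded into one hazard ratio. An inert drug could look active, or an active drug inert. The placebo patients met the same entry criteria and have the same central reading, but SAP 4.2.2.1 does not use them for this purpose. At stake is the interpretation of a stated secondary objective, not the trial's main conclusion.

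**Working it through.** The plan gives no sample size, expected hazard ratio or power for this comparison, so there is no figure to reproduce. The steps below show what the planned model can and cannot identify.

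**1. What the model estimates.** With two records per patient and strata defined by patient ID, let a be the pairs in which the on-study event comes first and b those in which the prior-therapy event comes first. Then HR = a/b and SE(log HR) = sqrt(1/a + 1/b).

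**2. Identification.** Under proportional hazards, the selinexor-only HR = drug HR × background HR, where the background holds line of therapy, selection and assessment. An observed 0.70 fits 0.70 × 1.0 and 1.0 × 0.70 equally well. Selinexor data alone cannot choose between them.

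**3. Arm adjustment in the protocol.** Arm is the same for both records of a patient, so an arm main effect cancels within every patient-ID stratum. Only a record-by-arm interaction, or separate models by arm, gives the control contrast.

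**4. Size, under assumptions.** SAP 1.1 gives 285 Phase 3 patients randomised 2:1, so about 190 selinexor and 95 placebo pairs. Assume that 50%, 70% or 90% of pairs are informative, that the drug has no effect, and that the background HR is g. With d = 190 × share, a = d·g/(1+g) and b = d/(1+g), the chance of nominal one-sided p<0.025 favouring selinexor is Φ(−ln g / SE − 1.96).

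Example 1: g = 0.8, share 50%. d = 95, a = 42.2, b = 52.8, SE = 0.206; Φ(0.223/0.206 − 1.96) = Φ(−0.88) = 0.19.

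Example 2: g = 0.7, share 90%. d = 171, a = 70.4, b = 100.6, SE = 0.155; Φ(0.357/0.155 − 1.96) = Φ(0.34) = 0.63.

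| Background HR | 50% informative | 70% | 90% |
|---|---|---|---|
| 1.0 | 0.025 | 0.025 | 0.025 |
| 0.9 | 0.074 | 0.088 | 0.102 |
| 0.8 | 0.190 | 0.248 | 0.305 |
| 0.7 | 0.402 | 0.526 | 0.631 |

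**5. Direction.** A simulation with no drug effect assumed exponential TTP, equal medians of 8, 12 or 20 weeks in both records, and 6-week on-study scans throughout (a simplification, since the real schedule widens after week 24).

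- Same scan interval in both records, no selection: HR 1.00, with non-informative on-study censoring present.
- Patients with prior TTP over 52 weeks absent: HR 0.70 to 0.97. Over 26 weeks absent: 0.37 to 0.75.
- Prior-therapy scans every 8 weeks: HR 1.13 to 1.45. Every 12 weeks: 1.34 to 2.26.

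The cut-offs and prior scan intervals are assumptions, not figures from the documents. They show only that the sign is not known in advance.

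**6. Precision with the placebo arm added.** At a true HR of 1, each arm's variance is 4/d, and the log ratio of the two HRs has SE = sqrt(4/d_sel + 4/d_pbo).

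- 50% informative: sqrt(4/95 + 4/47.5) = 0.355, 95% factor exp(1.96 × 0.355) = 2.01.
- 70%: sqrt(4/133 + 4/66.5) = 0.300, factor 1.80.
- 90%: sqrt(4/171 + 4/85.5) = 0.265, factor 1.68.
- Phase 2 (27 selinexor, 30 placebo), all pairs informative: sqrt(4/27 + 4/30) = 0.53, factor about 2.8, and wider with fewer informative pairs.

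**The case against.** The best defence is that the trial already has a sound estimate of the drug's effect on progression: randomised PFS, and a randomised between-arm TTP comparison under protocol 14.3.4.2 and the general rule in SAP 4.2. The objective is literally to compare two TTPs in the same patient, and the planned model does so. TTP is no longer a key secondary endpoint (SAP 1.8), and no text says this hazard ratio will be credited to selinexor. Randomisation balances prior TTP in expectation, so a ratio of within-patient hazard ratios largely re-estimates the randomised TTP effect, less directly and less precisely. All of this stands. It limits the consequence and argues against making that ratio the headline result. It does not explain why TTP is treated differently from TTNT, or why the departure from the protocol is unrecorded. Because SAP 4.2.2.1 lists placebo TTP only as exploratory, a reader may also doubt whether the general rule in SAP 4.2 still applies.

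Four stronger readings are tempting and are not supported:

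- A reader might infer that the trial cannot isolate a drug effect on progression. The randomised comparisons do that.
- A reader might size the bias from the Phase 2 counts in the protocol synopsis: "there were 48 events by WHO (22 selinexor, 26 placebo) and 28 events by RECIST v.1.1", giving 28/48 = 0.58. That is a ratio of event counts at one data cut, not a hazard ratio, and the WHO count is nearly saturated (48 of 49 patients). Nothing says that prior progression was read by WHO criteria.
- A reader might blame the on-study censoring rules as such. Non-informative censoring alone left the paired hazard ratio at 1.00.
- A reader might expect the placebo arm to remove all bias. It removes what the arms share, but not censoring at blinded discontinuation plus 30 days if that differs by arm.

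**Conclusion.** The point holds for the analysis it names. A selinexor-only paired hazard ratio mixes drug effect with line of therapy, entry selection and mode of assessment, and its bias could run in either direction. If the background hazard ratio were 0.7 to 0.8 and the drug had no effect, the analysis would reach nominal one-sided p<0.025 about 19% to 63% of the time. Those figures rest on an assumed background, 190 pairs and 50% to 90% informative pairs. They illustrate the risk and do not estimate the actual bias.

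The restriction also departs from what the protocol's wording implies and from the SAP's own TTNT analysis, without being listed as a change. Primary PFS, the OS hierarchy, type I error and the randomised TTP comparison are untouched. This is a cheap improvement to how one secondary objective is analysed and labelled.

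**What to change.** In SAP 4.2.2.1:

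- Run the same patient-stratified Cox model in the placebo arm for Ph3-ITT and Ph2-ITT, as SAP 4.2.2.5 does for TTNT in Ph3-ITT.
- Report the two arm-specific hazard ratios side by side, with the record-by-arm interaction (the ratio of hazard ratios) as a supportive contrast. Do not rely on an arm main effect.
- Label the selinexor-only hazard ratio as descriptive.
- State that the randomised between-arm TTP comparison is the estimate of drug effect on TTP. This also settles whether the general rule in SAP 4.2 applies.

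In SAP 1.7, list the departure from protocol 14.3.4.2.2.

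The cost is SAP wording and a small amount of programming. Prior-therapy history is already collected from every patient (protocol 10.3), so no new data are needed. The drawback is imprecision: a 95% interval factor of about 1.7 to 2.0 for the ratio in Phase 3, and about 2.8 or wider in Phase 2, which should be stated with the result.

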4.2.2.2. QLQ-C30

QLQ-C30 contains 30 questions and includes five functional scales (Physical, Role, Emotional, Social, and Cognitive Functioning), three symptom scales (Fatigue, Nausea/Vomiting and Pain) and a Global Health Status/QoL scale, and six single-item symptom items (dyspnoea, insomnia, appetite loss, constipation, diarrhoea and financial difficulties). The principle for scoring these scales is the same: 1. Calculate the mean of the items that contribute to the scale; this is the raw score. 2. Use a linear transformation to standardise the raw score, so that scores range from 0 to 100.

For functional scales and the global health status/QoL, a higher score represents a better level of functioning (better health status); for symptom scales/items, a higher score represents a higher level of symptomatology/problems (worse health status).

The missing data will be handled based on EORTC QLQ-C30 scoring manual (Fayers et al., 2001). The raw score (mean of the items that contribute to the scale) will only be calculated if at least half of the items (i.e., 3 of 6 items, or 3 of 5 items) from the domain have been answered. As a result, none of the single-item measures will be imputed.

The actual value and change from baseline before initiating a new antineoplastic treatment will be summarized using descriptive statistics over time for each of the five functional scales, three symptom scales and six items, and the global health status/QoL scale.

QLQ-C30 analyses will be summarized by treatment arm among Ph3-ITT, Ph3-PP, and Ph2-ITT populations. For exploratory purpose, QLQ-C30 will also be summarized in Ph3-OL and Ph2-OL populations, in which changes from baseline will be calculated using baseline values for the open-label period, i.e., last assessment on or before the start of open-label treatment.

Table 4-2 Scoring the QLQ-C30 version 3.0

	Scale	Number of items	Item range*	Version 3.0 Item numbers	Function scales
Global health status / QoL					
Global health status/QoL (revised) [†]	QL2	2	6	29, 30	
Functional scales					
Physical functioning (revised) [†]	PF2	5	3	1 to 5	F
Role functioning (revised) [†]	RF2	2	3	6, 7	F
Emotional functioning	EF	4	3	21 to 24	F
Cognitive functioning	CF	2	3	20, 25	F
Social functioning	SF	2	3	26, 27	F
Symptom scales / items					
Fatigue	FA	3	3	10, 12, 18	
Nausea and vomiting	NV	2	3	14, 15	
Pain	PA	2	3	9, 19	
Dyspnoea	DY	1	3	8	
Insomnia	SL	1	3	11	
Appetite loss	AP	1	3	13	
Constipation	CO	1	3	16	
Diarrhoea	DI	1	3	17	
Financial difficulties	FI	1	3	28	

* Item range is the difference between the possible maximum and the minimum response to individual items; most items take values from 1 to 4, giving range = 3.

† (revised) scales are those that have been changed since version 1.0, and their short names are indicated in this manual by a suffix “2” – for example, PF2.

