7.5.3. QoL Endpoint (Secondary Endpoint)

[figure not shown]
- QoL as measured by the EORTC QLQ-C30 total score and EuroQoL EQ 5D 5L category scores and total score.

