14.3.7. Procedures for Handling Missing Data

No imputation of missing efficacy data is planned for the primary analysis of efficacy endpoints. For patient reported QoL measurements, missing data will be handled as described in the *EORTC-QLQ-C30* and *EuroQoL EQ-5D-5L Scoring Manuals*. Additional sensitivity analyses will be done using the Jump to Reference (J2R) and last observation carried forward imputation approaches.

For time to event analyses, patients who have no efficacy evaluations will be considered as censored at time 0. For OS, patients will be censored on the date they were last known to be alive regardless of disease status.

For AEs, missing dates will not be imputed; however, if partial dates are available, they will be used to assess if the AE occurred during the treatment period. Missing severities of AEs will not be imputed and will be considered missing in any tabulations of AE severity. If an AE is missing a response to the question regarding relationship to treatment, the event will be considered to be related.

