4.2.2.3. EQ-5D-5L

The EQ-5D-5L is a validated quality of life questionnaire developed by the EuroQol group in order to provide a simple, generic utility measure for characterizing current health states of patients. It consists of 2 parts, the descriptive system and the visual analogue scale (VAS).

EQ-5D-5L descriptive system comprises 5 dimensions: mobility, self-care, usual activities, pain/discomfort, and anxiety/depression. Each dimension has 5 levels (no problems, slight problems, moderate problems, severe problems and extreme problems). EQ-5D-5L health states, defined by the EQ-5D-5L descriptive system, will be converted into a single index value according to the U.S. population (van Hout et al, 2012). The VAS records the respondent's self-rated health status on a vertical visual analogue scale. The VAS 'thermometer' has 100 (best imaginable health state) at the top and 0 (worst imaginable health state) at the bottom.

The actual value and change from baseline before initiating a new antineoplastic therapy will be summarized using descriptive statistics over time for EQ-5D-5L health states and VAS.

EQ-5D-5L analyses will be summarized by treatment arm among Ph3-ITT, Ph3-PP, and Ph2-ITT populations. For exploratory purpose, EQ-5D-5L will also be summarized in Ph3-OL and

Ph2-OL populations, in which changes from baseline will be calculated using baseline values for the open-label period, i.e., last assessment on or before the start of open-label treatment.

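### The SAP replaces the protocol's quality-of-life mixed model and its J2R and LOCF analyses with descriptive summaries, and SAP 1.7 does not record the change

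*SAP*

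**What the plan says.** **Protocol v9.0.** Section 7.5.3 defines the endpoint as "QoL as measured by the EORTC QLQ-C30 total score and EuroQoL EQ 5D 5L category scores and total score". Section 14.3.4.2.2 says that it "will be analyzed as a total score, using a linear mixed effects model with fixed effect of treatment arm, randomization stratification factors", with the baseline value as a covariate, a random subject effect and repeated measures over time. On the choice of score it adds "For EORTC QLQ-C30 the transformed score will be used", following the EORTC scoring manual, and "For the EuroQoL EQ-5D-5L questionnaire, the overall health score will be used". Section 14.3.7, directly after its sentence on missing QoL items, adds: "Additional sensitivity analyses will be done using the Jump to Reference (J2R) and last observation carried forward imputation approaches".

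**SAP.** Section 1.7 states that the SAP rests on Protocol v9.0. For QLQ-C30, section 4.2.2.2 says "The actual value and change from baseline before initiating a new antineoplastic treatment will be summarized". It specifies that these quantities "will be summarized using descriptive statistics over time for each of the five functional scales", and likewise for the symptom scales, the single items and the global scale. For EQ-5D-5L, section 4.2.2.3 says that the same quantities "will be summarized using descriptive statistics over time for EQ-5D-5L health states and VAS". Section 2.2 bases continuous summaries on observed values only. Section 2.2.7 leaves missing QoL data to the two scoring manuals and goes no further.

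**The concern.** QoL is a Phase 3 secondary objective in both documents. The protocol gives it a comparative analysis, and the SAP takes that analysis away without saying so.

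The two approaches are not interchangeable here. Under Protocol Table 1, questionnaires are completed at screening, on Day 1 of each cycle from Cycle 2, and at the end-of-blinded-treatment visit, but not during survival follow-up. Blinded treatment stops at centrally read progression. Observed means at later visits therefore describe only the patients still on blinded treatment, a group selected by progression and tolerability, and the selection may differ between arms. The baseline-adjusted model with J2R and LOCF was the protocol's means of examining that. With descriptive tables alone, no arm difference is designated as the QoL result, and nothing shows how sensitive the picture is to dropout.

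The omission also leaves a gap in documentation. Protocol sections 14 and 14.4 call for reporting of departures from the statistical plan. An analysis that follows the SAP is not such a departure, so SAP 1.7 is the natural place for this change to be recorded.

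**Working it through.** The plan gives no figure to reproduce. The check is a comparison of passages plus one count.

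**1. What was planned and what remains.**

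| Element | Protocol v9.0 | SAP |
|---|---|---|
| Model for QLQ-C30 | Linear mixed model (14.3.4.2.2) | None; descriptive (4.2.2.2) |
| Model for EQ-5D-5L | Linear mixed model (14.3.4.2.2) | None; descriptive (4.2.2.3) |
| Baseline adjustment | Baseline value as covariate | Change from baseline tabulated only |
| Missing items | Scoring manuals (14.3.7) | Scoring manuals (2.2.7) |
| Sensitivity analyses | J2R and LOCF (14.3.7) | Neither: 0 of 2 |

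SAP 4.2 does not fill the gap. It sets methods for time-to-event endpoints and for dichotomous endpoints, and none for a continuous score measured repeatedly.

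**2. Whether the change is recorded.** SAP 1.7 lists two kinds of modification: endpoints dropped because data are unavailable, and a new Ph3-PP definition. Its redacted bullets cannot cover QoL, because SAP 1.7 says that the dropped endpoints are all exploratory apart from one Phase 2 secondary endpoint, which it names (the six-week FDG-PET and CT assessment). Phase 3 QoL is a secondary objective (SAP 1.2.2.2). SAP 1.8 does not mention QoL.

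**3. Whether the model can be restored exactly as the protocol words it.** SAP Table 4-2 gives:

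- scores: 1 global + 5 functional + 3 symptom scales + 6 single items = 15
- items: 2 + (5 + 2 + 4 + 2 + 2) + (3 + 2 + 2) + 6 = 2 + 15 + 7 + 6 = 30

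The 30 items match the 30 questions stated in SAP 4.2.2.2. Every item is used, and no total is listed. High symptom scores mean worse health and high functional scores mean better health, so a total would need a rule for reversing or weighting. The protocol's pointer to the transformed score does not say which scale is meant. For EQ-5D-5L, the protocol's overall health score is not matched to either of the SAP's two quantities, the index and the VAS. One score per questionnaire has to be named.

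**4. The contrast.** The protocol lists model terms but no estimate to report. It lists no arm-by-visit term, so an arm effect averaged over visits fits the stated terms most directly. A difference at one visit would need that interaction to be added.

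**The case against.** **A descriptive analysis is legitimate for a non-key secondary endpoint.** This stands. QoL is outside the testing hierarchy in SAP 4.4, and the sponsor may choose to describe it. An unadjusted difference could even be worked out from the tabulated means and standard deviations. But none is planned or named as the result, and a choice that departs from the protocol should be recorded.

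**The method may be in text that cannot be seen.** SAP section 2 sends a redacted topic to a separate plan, and SAP 4.3 is redacted. QoL is unlikely to be in either, since its methods are set out in 4.2.2.2 and 4.2.2.3.

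**The J2R and LOCF sentence may reach beyond QoL.** It may, but the SAP omits both analyses on either reading.

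**The scores are less obscure than they look.** This is partly right. Protocol 10.7.1 says that EQ-5D-5L yields a descriptive profile and a single index value, which plausibly explains the category and total scores of 7.5.3. Only the overall health score then stays unclear. For QLQ-C30, the scoring manual is not available here. The documents show only that they contain no construction rule. The total score is the protocol's term, and the SAP never uses it. Nor should the count of 15 be read as 15 candidate totals, since it includes single symptom items.

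**A reader might infer that the SAP contradicts itself on open-label selinexor, so that placebo and selinexor periods would be mixed in the QoL data.** The documents do not support that. SAP 4.1.1, 4.2.1.1 (one OS sensitivity analysis) and 4.2.2.4 count open-label selinexor as new therapy. The two statements that it is not (SAP 2.4 and 5.1.1.1) apply only to selinexor-arm patients who continue. For placebo crossover patients, SAP 2.4 ends the blinded period before the first open-label dose, SAP 2.6 sets a separate open-label baseline, and the QoL sections summarize Ph3-OL separately. What remains is that the QoL sections do not cite SAP 2.4.

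**Conclusion.** The point holds. A protocol-specified model for two questionnaires and both missing-data sensitivity analyses are missing from the visible SAP, and SAP 1.7 does not record the change. The Phase 3 QoL objective is left without a planned baseline-adjusted arm difference, a CI or a check on dropout.

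The effect on the QoL findings cannot be given in size or direction, because the documents do not state how many patients contribute at each visit. PFS, OS, type I error and sample size are unaffected. The correction is therefore one that should be made because it is cheap and restores the sponsor's own plan. It does not bear on the trial's main conclusions. The verdict assumes that the redacted separate plan and SAP 4.3 do not hold the QoL model.

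**What to change.** Amend the SAP only, before unblinding.

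- In 4.2.2.2 and 4.2.2.3, restore the protocol's mixed model in Ph3-ITT with its stated terms, for one named QLQ-C30 score (for example Global Health Status/QoL) and one named EQ-5D-5L score (the index or the VAS). State which protocol terms these scores stand for.
- Report the arm difference with a 95% CI for a contrast named in advance, either averaged over visits or at one visit.
- Add the J2R and LOCF sensitivity analyses, and keep all other scores descriptive.
- Record and justify in SAP 1.7 any departure that remains, including a decision to stay descriptive.
- As a minor clarification, have the QoL sections cite the SAP 2.4 periods. The cut-off for placebo crossover patients is then the start of open-label selinexor, and selinexor-arm continuers follow the SAP 2.4 rule.

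The cost is SAP wording, one model for each of two scores, the J2R and LOCF reruns and a few tables. The data and covariates are already collected, no protocol amendment is needed, and alpha and sample size do not change. The downside is modest extra programming and output.
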